6.5 Measures to be Taken to Avoid or Minimize Bias

This preliminary, prospective, single-arm study is intended to collect information regarding the safety and potential efficacy of intrasphincteric injection of AMDC-USR for the treatment of male SUI that develops following prostate surgery. Study patients will be enrolled at up to 5 sites and uniform definitions will be used for study endpoints.

7.0 Methods

7.1 Patient Assessment and Screening

Male patients who present with SUI symptoms that developed following prostate surgery that occurred at least 12 months prior to enrollment may be considered for participation in this study.

7.2 Patient Consent

Patients who appear to meet the inclusion criterion and none of the exclusion criteria will be invited to participate in this study. All patients eligible for entry into the study will have the clinical study, as well as potential risks and benefits of their participation in the study, explained to them. Each patient who agrees to participate will be required to sign and date an informed consent document prior to any study-specific testing or procedure. If new information is obtained during the clinical study, any patient who has not exited the study will be informed about the new information, and will be re-consented at the discretion of the investigator or the site's IRB/REB.

7.3 Pre-enrollment (Visit 1) – Screening

Screening tests may be completed in up to 3 screening visits to accommodate site-specific scheduling. It is recommended that screening tests conducted in Visit 1 be completed within 8 weeks preceding the biopsy visit. Bloodborne pathogen testing must be completed within 30 days before the biopsy procedure. If more than one visit is required, adverse events that occur after the patient signs the consent form shall be recorded during subsequent visits.

After providing informed consent, the patient will have a medical history (including a urinary incontinence-focused history), a physical examination (including assessment of vital signs), a clinical assessment, and a medication assessment. Urine samples will be collected to test for nitrites and leukocyte esterase. If the urine test is positive for leukocyte esterase or nitrites, then a

urine culture may be performed. The patient will undergo a bladder stress test (please refer to Appendix A for the Instructions for the Bladder Stress Test) and will complete a 24-hour pad test. Patients will be instructed on how to perform the 24-hour pad test (please refer to Appendix B for the Instructions for the 24-Hour Pad Test) and will be provided with sufficient preweighed pads to complete the test. The completed 24-hour pad test must be returned before or at the next scheduled screening visit. A PVR urine volume will be measured with ultrasound/bladder scan. Patients will complete the following questionnaires: ICIQ, IQOL, PGI-S, I-PSS, and IIEF-5. Blood samples will be collected to assess for PSA levels, bloodborne pathogens, hematocrit, hemoglobin, WBC count, blood urea nitrogen (BUN) or urea, and creatinine. Patients will undergo cystoscopy for evaluation of the appearance of urethral and bladder tissue. An existing cystoscopy evaluation can be used if performed within 6 months prior to the time of consent. It is recommended that screening tests be performed from the least invasive test to the most invasive. Adverse events reported by the patient after informed consent is obtained will be recorded.

7.4 Point of Enrollment

Patients are considered enrolled in the study at the time of the biopsy procedure.

7.5 Medications

Patients may be given medication (including for pain or anxiety) according to each institution's standard of care or at the physician's discretion. Additionally, patients should be maintained on a stable dose or frequency of medication known to affect lower urinary tract function or erectile dysfunction, including but not limited to, anticholinergics, beta 3 adrenergic receptor agonists, tricyclic antidepressants, SNRI or SSRI antidepressants, diuretics, or alpha-adrenergic blockers, or phosphodiesterase type-5 inhibitors, for at least 2 weeks prior to screening assessments and throughout the study. A course of prophylactic antibiotics will be given prior to the injection procedure.

7.6 Biopsy (Visit 2)

After patient eligibility is confirmed, patients will return to the clinic for an outpatient procedure in which muscle tissue is obtained using a needle biopsy technique. Note that several passes of the biopsy needle may be required to obtain a satisfactory sample of muscle tissue. Additionally, if the first biopsy does not produce an adequate sample for product isolation, it may be necessary for the patient to return for another biopsy procedure. The maximum permissible number of

biopsy needle passes, and the total number of biopsies, is contingent upon patient tolerance and the satisfactory procurement of muscle tissue. If the biopsy procedure is scheduled for more than 30 days after the most recently completed bloodborne pathogen tests, the bloodborne pathogen tests (i.e., Hepatitis B, Hepatitis C, HIV, and Syphilis) must be repeated before the biopsy procedure to confirm the patient's continued eligibility for study participation. Additionally, the medication log will be updated if necessary. Any adverse events occurring since the last visit or before, during, or after the biopsy procedure will be recorded and reported as appropriate.

7.6.1 Post-Biopsy Follow-up (Phone)

Within 5 business days after the biopsy procedure, patients will be contacted by phone to determine whether any adverse events have occurred and whether any updates to the medication log are necessary.

7.7 Procedure (Visit 3) – Treatment Day 0

Approximately 12-13 weeks after the muscle biopsy, patients will return to the clinic for a brief outpatient procedure. At the start of the visit or before the visit, patients will provide a completed 24-hour pad test and complete the ICIQ, IQOL, PGI-S, I-PSS, IIEF-5 questionnaires. The 24-hour pad test and questionnaire data collected on the day of injection will be used as the baseline data. Prophylactic antibiotics will be given prior to the injection procedure. Prior to injection, patients will have a urine sample collected to test for nitrites and leukocyte esterase. If the urine test is positive for leukocyte esterase or nitrites, a urine culture must be performed and the injection will be delayed. A negative urine dipstick for leukocyte esterase and nitrites is required in order to undergo AMDC-USR injection. Ultrasound may be performed to aid in the injection procedure. Under direct vision, multiple injections will be performed to circumferentially distribute AMDC-USR within the striated muscle of the urethral sphincter. After the injection is completed, the injected area will be examined for any excessive bleeding or excessive trauma. Prior to discharge, patients will demonstrate a normal void and will have their PVR urine volume determined by ultrasound/bladder scan. The medication log will be updated if necessary. Any adverse events occurring since the last visit or before, during, or after the injection procedure will be recorded and reported as appropriate.

7.8 Follow-up

Follow-up windows are intended as recommendations only. They are not absolute and are not intended to limit data collection due to scheduling conflicts.

7.8.1 Post-Treatment Follow-up (Phone) – Treatment Day 1-2

Within 2 business days after treatment, patients will be contacted by phone to determine whether any adverse events have occurred and whether any updates to the medication log are necessary.

7.8.2 Post-Treatment Follow-up (Phone) – Treatment Week 1 Within five business days after treatment, patients will be contacted by phone to determine whether any adverse events have occurred and whether any updates to the medication log are necessary.

7.8.3 Follow-up (Visit 4) – Treatment Month 1 (\pm 1 week)

A clinical assessment will be performed. Patients will provide a completed 24-hour pad test, and will have a urine sample collected to test for nitrites and leukocyte esterase. If the urine test is positive for nitrites or leukocyte esterase, then it is recommended a urine culture be performed. Blood samples will be collected to assess PSA levels, hematocrit, hemoglobin, WBC count, BUN or urea, and creatinine. PVR urine volume will also be determined via ultrasound/bladder scan. If, after multiple void attempts, the PVR volume is \geq 200 mL, additional evaluation for obstruction is recommended. During the visit, patients will complete the following questionnaires: ICIQ, IQOL, PGI-S, I-PSS, IIEF-5, and PGI-I. The medication log will be updated if necessary. Any adverse events occurring since the last contact will be recorded and reported as appropriate.

7.8.4 Follow-up (Visit 5) – Treatment Month 3 (\pm 1 week)

A clinical assessment will be performed. Patients will provide a completed 24-hour pad test, and will have a urine sample collected to test for nitrites and leukocyte esterase. If the urine test is positive for nitrites or leukocyte esterase, then it is recommended a urine culture be performed. PVR urine volume will also be determined via ultrasound/bladder scan. If, after multiple void attempts, the PVR volume is \geq 200 mL, additional evaluation for obstruction is recommended. During the visit, patients will complete the following questionnaires: ICIQ, IQOL, PGI-S, I-PSS, IIEF-5, and PGI-I. The medication log will be updated if necessary. Any adverse events occurring since the last visit will be recorded and reported as appropriate.

7.8.5 Follow-up (Visit 6) – Treatment Month 6 (- 2, + 4 weeks)

A clinical assessment will be performed. Patients will provide a completed 24-hour pad test, and will have a urine sample collected to test for nitrites and leukocyte esterase. If the urine test is positive for nitrites or leukocyte esterase, then it is recommended a urine culture be performed. PVR urine volume will also be determined via ultrasound/bladder scan. If, after multiple void attempts, the PVR volume is ≥ 200 mL, additional evaluation for obstruction is recommended. During the visit, patients will complete the following questionnaires: ICIQ, IQOL, PGI-S, I-PSS, IIEF-5, and PGI-I. The medication log will be updated if necessary. Any adverse events occurring since the last visit will be recorded and reported as appropriate.

7.8.6 Follow-up (Visit 7) – Treatment Month 12 (- 2, + 4 weeks)

A clinical assessment will be performed. Patients will provide a completed 24-hour pad test, and will have a urine sample collected to test for nitrites and leukocyte esterase. If the urine test is positive for nitrites or leukocyte esterase, then it is recommended a urine culture be performed. Blood samples will be collected to assess PSA levels, hematocrit, hemoglobin, WBC count, BUN or urea, and creatinine. PVR urine volume will also be determined via ultrasound/bladder scan. If, after multiple void attempts, the PVR volume is ≥ 200 mL, additional evaluation for obstruction is recommended. The patient will undergo a bladder stress test and have a cystoscopy (for evaluation of the appearance of the urethral tissue). During the visit, patients will complete the following questionnaires: ICIQ, IQOL, PGI-S, I-PSS, IIEF-5, and PGI-I. The medication log will be updated if necessary. Any adverse events occurring since the last visit will be recorded and reported as appropriate.

7.8.7 Post-Treatment Follow-up (Phone) – Treatment Month 24 (-2, +4 weeks)

24 months after treatment, patients will be contacted by phone to determine whether any adverse events have occurred and whether any updates to the medication log are necessary.

7.9 Duration of Study and Patient Participation

Patients are expected to participate in this study for approximately 2.5 years from the time of the first screening visit. This duration includes time for screening, biopsy, injection, and 24 months of follow-up.

7.10 Criteria and Procedures for Withdrawal

A patient may decide to withdraw from the study at any time either before or after undergoing study procedures without prejudice or loss of care. The patient should notify the investigator of his desire to withdraw. The investigator will notify the sponsor. The investigator may also decide to withdraw a patient from the study at any time based on medical judgment. In all instances of withdrawal, data collected up to the time of patient withdrawal, including the study exit form and the appropriate study visit, shall be submitted to the data coordinating center and shall include the reason why the patient has been withdrawn from the study. Patients will be asked to allow access to their medical records for 30 days after the date of withdrawal. Any data collected on the patient up to the point of withdrawal plus 30 days may be used in the study.

In the event a patient cannot be contacted for post-treatment assessments, at least 3 attempts may be made to locate the patient, and these efforts will be documented. If the patient cannot be located, a lost to follow-up entry will be submitted.

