2.0 Objectives of the Clinical Study

2.1 Primary Objectives

The primary objective of this study is to evaluate the safety of AMDC-USR during the

24 months following treatment of SUI in male patients who have undergone prior prostate surgery.

Safety will be determined by the frequency and severity of adverse events related to study procedures and study product through 24 months following treatment of SUI in male patients who have undergone prior prostate surgery. PVR volume will be assessed through 12 months post-treatment to monitor potential retention or obstruction.

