6.3 Endpoints

6.3.1 Primary Endpoints

The primary safety endpoints include:

- Study product-related SAEs reported through 24-month follow-up;

- Study product-related, biopsy procedure-related, and injection procedure-related adverse events reported through 24-month follow-up; and
- PVR urine volume reported through 12-month follow-up.

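### Sections 7.10 and 7.11 make every withdrawal a full exit with data capped at 30 days, so an injected man withdrawn before about month 11 loses over half of the 24-month primary safety window

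*Combined protocol and SAP*

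**What the plan says.** **Safety horizon.** Section 2.1 sets the primary objective: "Safety will be determined by the frequency and severity of adverse events related to study procedures and study product through 24 months following treatment". Section 6.3.1 lists as a primary endpoint "Study product-related SAEs reported through 24-month follow-up", and adverse events related to product, biopsy or injection over the same period.

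**Who may withdraw a man.** Under Section 7.10 the patient may leave at any time, and "The investigator may also decide to withdraw a patient from the study at any time based on medical judgment".

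**What follows.** One procedure covers both routes. "In all instances of withdrawal, data collected up to the time of patient withdrawal, including the study exit form and the appropriate study visit" are sent to the data coordinating center with the reason. Then "Patients will be asked to allow access to their medical records for 30 days after the date of withdrawal", and "Any data collected on the patient up to the point of withdrawal plus 30 days may be used in the study". Section 7.11 lists withdrawal among the events that end participation.

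**Men who cannot be reached.** Section 7.10 says "at least 3 attempts may be made to locate the patient, and these efforts will be documented", after which the man is entered as lost to follow-up.

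**Late contact.** Section 7.8.7 says "24 months after treatment, patients will be contacted by phone to determine whether any adverse events have occurred". This call is the only scheduled contact after month 12.

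**The concern.** The treatment is a single injection, so an injected man stays exposed whether or not he remains in the study. The primary question is what happens to him over 24 months. Section 7.10 nevertheless closes his data 30 days after withdrawal, whoever decided it and for whatever reason. Neither section offers an intermediate status in which visits and tests stop but the safety phone call or records review continues.

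Two things are at stake. First, related events that occur after the cap go uncounted in a primary endpoint. Second, withdrawal on medical judgment could fall more often on men with complications, in which case the missing follow-up would be informative. With at most 30 treated men, one missed related SAE is the difference between 1/30 (3.3%) and 0/30.

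There is also an ambiguity. The plan does not say how to classify a man who declines further clinic visits, pad tests or cystoscopy but is willing to be telephoned. A site could record him as withdrawn and so trigger the cap.

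**Working it through.** The plan gives no sample-size calculation, power or dropout rate (Sections 8.1 and 8.2), so there is no figure of its own to reproduce.

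**Step 1. Inputs.** Safety window: 24 months (Sections 2.1 and 6.3.1). Data after withdrawal: 30 days (Section 7.10), which is 30 / (365.25/12) = 0.99 month. Treated men: up to 30 (Section 8.2).

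**Step 2. Share of the window lost by one injected man.** For withdrawal at month t, follow-up is covered to t + 0.99, and the share lost is (24 − t − 0.99) / 24.

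| Withdrawal month | Covered to month | Months lost | Share lost |
|---|---|---|---|
| 1 | 1.99 | 22.01 | 92% |
| 3 | 3.99 | 20.01 | 83% |
| 6 | 6.99 | 17.01 | 71% |
| 9 | 9.99 | 14.01 | 58% |
| 12 | 12.99 | 11.01 | 46% |
| 18 | 18.99 | 5.01 | 21% |

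Half is lost when t + 0.99 = 12, that is, at t = 11.01. These figures assume the man agrees to the 30 days of records access. If he declines, a further 0.99/24 = 4% of the window is lost.

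**Step 3. Study level (number and timing of withdrawals assumed).** Planned follow-up is 30 × 24 = 720 patient-months. If k men withdraw at month 6, the loss is k × 17.01 / 720:

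- k = 1: 2.4%
- k = 3: 51/720 = 7.1%
- k = 6: 102/720 = 14.2%

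**Step 4. Precision.** Suppose a complete-case analysis drops these men and no related SAE is seen in the rest. The exact two-sided 95% upper limit is 1 − 0.025^(1/n): 11.6% for n = 30, 11.9% for n = 29, 12.8% for n = 27 and 14.2% for n = 24. The loss of precision is modest. The more important question is whether the men lost differ from those kept.

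**Step 5. Does another section restore the follow-up?**

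- Section 7.8 treats visit windows as recommendations. That helps men still in the study, not men who have exited.
- Section 12.0 has adverse events followed under institutional standard of care. It does not extend the period that Section 7.10 sets for using data after withdrawal.
- Section 8.3 allows Kaplan-Meier or Cox methods if data are censored, and Section 8.4 allows complete-case analysis or multiple imputation. All are optional. In their standard forms they assume that loss is unrelated to the unseen outcome.

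None of these brings back the follow-up that the cap removes.

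**The case against.** **Stopping visits is not withdrawal.** A reader might infer that a man who merely stops attending loses his safety follow-up. The documents do not support that. Section 7.10 concerns withdrawal from the study, and a reachable man who has not withdrawn is still due the month-24 call. What stands is that the plan does not separate the two situations.

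**The loss depends on timing.** A reader might infer that every withdrawal costs most of the window. It does not: the loss is under half from about month 11 onward, and 21% at month 18. Enrollment is at biopsy (Section 7.4) and injection follows about 12-13 weeks later (Section 7.7), so a man withdrawn in between has no post-injection window to lose.

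**Medical withdrawal has other purposes.** A reader might infer that, with a single injection, it can only end observation. It can also release a man from the month-12 cystoscopy and stress test, from the stable-medication requirement and from the bar on penile clamps. This objection stands, but none of these purposes requires safety contact to end.

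**The triggering event is captured.** The reason for withdrawal and the data to that point must be submitted, and 30 more days may be used. This stands. The exposure is to later or delayed related events only.

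**Bias is not shown.** A reader might infer that the 24-month counts are biased low. The documents give neither a dropout rate nor reasons for withdrawal, so this is a possibility only. The study is also descriptive and unpowered. That weakens any argument from precision, but safety ascertainment is its stated purpose.

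**Consent wording is not available here.** Any provision in it for later contact cannot be checked. The 30-day text in Section 7.10 stands as written.

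**Conclusion.** The point holds in a limited form. Sections 7.10 and 7.11 apply one full exit to every withdrawal, cap records access and usable data at 30 days, and provide no reduced-follow-up category, while two of the three primary endpoints run through 24 months. The loss for an injected man is about 92%, 83%, 71%, 58%, 46% or 21% of the window for withdrawal at month 1, 3, 6, 9, 12 or 18. These shares follow from the plan's own figures.

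The study-level figures (2.4% to 14.2% of patient-months) rest on an assumed one to six withdrawals at month 6. That the 24-month counts may be too low rests on a further assumption: that medical withdrawals fall on men with complications who go on to have later related events. The change is worth making because it protects a primary endpoint at little cost, not because bias has been demonstrated.

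**What to change.** In Section 7.10, for injected men, define two levels:

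- **(a)** stopping clinic visits and tests, or withdrawal decided by the investigator;
- **(b)** the patient's own withdrawal from all further contact and data use.

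For (a), with the man's agreement, keep the existing month-24 adverse event call and ask for records access through 24 months after injection in place of 30 days. Amend the sentence "Any data collected on the patient up to the point of withdrawal plus 30 days may be used in the study" and the withdrawal item in Section 7.11 to match. Level (b) preserves a man's right to refuse everything further.

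A minor, separate point concerns loss to follow-up: make the three contact attempts in Section 7.10 mandatory by changing 'may' to 'will'.

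The cost is a protocol and consent wording change and a few phone calls of a kind already scheduled. No visit or procedure is added. The downside is that some men will decline the longer access, and for them the loss remains.

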7.11 Participation Endpoints of the Study

A patient's participation in the study will end after any of the following:

- Patient completed all scheduled clinical evaluations to 24 months;
- Patient withdrew or was lost to follow-up;
- Patient received nonstudy treatment for SUI (e.g., injection of a bulking agent or completed surgery for a sling);
- Study closed; or
- Patient died.

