release specifications of purity and dose. If a product meets all predefined safety criteria, the product may be offered to the patient at the physician's discretion. Affected patients will be notified prior to their injection procedure and must provide consent of their willingness to receive an injection of product that does not meet all target criteria.

After reaching the desired concentration, the isolated and expanded AMDC-USR will be frozen and shipped back to the investigating physician. The physician will thaw the AMDC-USR and dilute the sample with an approximately equal volume of physiological saline. Under direct vision, the resulting suspension will be injected into the patient's urethral sphincter in a brief outpatient procedure.

Patients will be assessed for safety and improvement in urinary incontinence symptoms at 1, 3, 6 and 12 months following treatment. Adverse events will be assessed at all follow-up visits, as well as during follow-up calls at 1-2 days, 1 week, and 24 months. A study overview is depicted in Figure 1.1.

The primary safety measures will be the incidence of study product-related serious adverse events (SAEs) and the incidence of study product-related, biopsy procedure-related, and injection procedure-related adverse events and post-void residual (PVR) urine volume. Secondly, potential efficacy will be evaluated based on reduction in the amount of urine leakage, as assessed by a 24-hour pad test at 1, 3, 6, and 12 months following treatment. Changes in patient-reported incontinence symptom severity, quality of life (QOL), and erectile dysfunction (ED) symptoms will also be assessed at 1, 3, 6, and 12 months following treatment.

[figure not shown]

Figure 1.1. Study flow diagram

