6.0 Design of the Clinical Study

6.1 Design of Study

This preliminary, prospective, single-arm clinical study will evaluate the safety and potential efficacy of AMDC-USR for the treatment of male SUI that develops following prostate surgery.

The study will treat up to 30 patients (treated with 150×10^6 AMDC-USR) at up to 5 clinical sites. Enrollment is expected to be completed within 2.5 years of initiating the study. Patients will be followed for 24 months post-treatment. The first 3 patients at each site must reach 1-month follow-up before subsequent patients can be treated at that site.

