13.0 Early Termination or Suspension of the Clinical Study

Any decision to suspend enrollment or terminate the clinical study, either completely or at one or more clinical sites, will be made by the sponsor and, if appropriate, the local IRB/REB. If a decision is made to terminate the study, all patients who have undergone one or more study procedures (i.e., biopsy or injection) will be followed for 30 days following the most recent procedure. Regulatory authorities or the IRB/REB will be notified as required by local regulations.

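### Section 7.11 ends participation at non-study SUI treatment with no safety exception, although two primary safety endpoints run through 24 months

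*Combined protocol and SAP*

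**What the plan says.** The primary objective is safety over 24 months. Section 2.1 states: "Safety will be determined by the frequency and severity of adverse events related to study procedures and study product through 24 months following treatment". Section 6.3.1 carries this into the primary endpoints. The first is "Study product-related SAEs reported through 24-month follow-up", and the second, covering adverse events related to product, biopsy or injection, has the same horizon. The third, post-void residual volume, stops at Month 12. Section 6.1 adds, without qualification: "Patients will be followed for 24 months post-treatment".

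Adverse events are gathered at planned contacts. Section 1.0 says: "Adverse events will be assessed at all follow-up visits, as well as during follow-up calls at 1-2 days, 1 week, and 24 months". After the Month 12 visit one contact remains, described in 7.8.7: "24 months after treatment, patients will be contacted by phone to determine whether any adverse events have occurred".

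Section 7.11 lists the events that end participation. Completion, withdrawal or loss to follow-up, study closure and death are four of them. The fifth is: "Patient received nonstudy treatment for SUI (e.g., injection of a bulking agent or completed surgery for a sling". Nothing in 7.11 separates the end of efficacy assessment from the end of safety follow-up.

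**The concern.** A patient who has a bulking injection or a sling before Month 24 leaves the study under 7.11, while 2.1, 6.1 and 6.3.1 still call for 24 months of safety observation. For that patient the sections cannot all be followed. Such exits are foreseeable: inclusion criterion 4 in Section 6.2 requires that earlier therapy has not resolved symptoms acceptably, and 7.11 itself names the likely next treatments.

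Two things are at stake. First, two of the three primary endpoints would be observed for less than their stated period in these patients. Second, Section 8.3 promises 95% confidence intervals for all endpoint variables, but the plan does not say how a patient with truncated follow-up enters the incidence. Counting him as event-free to Month 24 would understate it.

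Section 7.11 does not mention adverse events, so the effect on their collection is an inference. Nothing bars a site from reporting a later event, but as written new events would probably not be sought.

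**Working it through.** **Does another section close the gap?**

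- Section 7.10 allows a further 30 days: "Any data collected on the patient up to the point of withdrawal plus 30 days may be used in the study". It is written for withdrawal, which 7.11 lists as a separate reason. Even if it applied, it would reach Month 24 only for exits in about the last month.
- Section 13.0 says patients "will be followed for 30 days following the most recent procedure", but only if the study is terminated.
- Section 12.0 deals with reporting events and following those already reported. It schedules no contact to find new ones.
- Section 8.3 permits Kaplan-Meier or Cox methods if data are censored, and 8.4 permits complete-case analysis or multiple imputation. Both are optional, and neither mentions these exits.

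None restores adverse-event collection to Month 24.

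**Contacts lost.** Table 6.1 has seven post-treatment contacts: Day 1-2, Week 1, and Months 1, 3, 6, 12 and 24. An exit just after the Month 12 visit loses one, the call covering 12 of the 24 months. An exit just after the Month 3 visit loses three.

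**Illustration of size.** The plan has no figure to reproduce; Sections 8.1 and 8.2 state that the study is unpowered and its sample size was not derived. From the documents: up to 30 treated patients, 24 months, hence 30 × 24 = 720 planned patient-months, and 95% intervals. Assumed: *k* exits at month *m*, with (*k*, *m*) = (3, 18), (6, 12) and (9, 3).

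1. Patient-months lost, *k*(24 − *m*):
   - 3 × 6 = 18; 18/720 = 2.5%
   - 6 × 12 = 72; 72/720 = 10.0%
   - 9 × 21 = 189; 189/720 = 26.3%

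2. Two-sided 95% upper limit for 24-month risk with zero events:
   - Exited patients censored, constant hazard: 1 − exp(−3.6889 × 24/PT), where 3.6889 = −ln 0.025 and PT is the observed patient-months (702, 648, 531). Full follow-up, PT = 720, gives 11.6%.
   - Exited patients excluded: the exact limit 1 − 0.025^(1/n), with n = 27, 24, 21.
   - Exited patients counted as event-free: n stays at 30.

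| Exits | Counted event-free | Censored | Excluded |
|---|---|---|---|
| 3 at Month 18 | 11.6% | 11.8% | 12.8% |
| 6 at Month 12 | 11.6% | 12.8% | 14.2% |
| 9 at Month 3 | 11.6% | 15.4% | 16.1% |

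3. If the 30 days in 7.10 are read as applying (one month added per exit), the losses are 15, 66 and 180 patient-months (2.1%, 9.2%, 25.0%). The censored limits become 11.8%, 12.7% and 15.1%.

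4. Understatement if exited patients are counted as event-free after exit, with an assumed true 24-month risk *r* = 10% in every patient. Expected reported incidence = [(30 − *k*)*r* + *k*(1 − (1 − *r*)^(*m*/24))]/30:
   - (27 × 0.10 + 3 × 0.0760)/30 = 9.8%
   - (24 × 0.10 + 6 × 0.0513)/30 = 9.0%
   - (21 × 0.10 + 9 × 0.0131)/30 = 7.4%

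**The case against.** The best defence is that this is a legitimate design choice. Through 24 months can be read as a planned maximum, since the same wording makes no exception for death, loss to follow-up or study closure either. The endpoints count only events related to product or study procedures, and attributing a local event becomes harder once a sling or bulking agent is in place. Stopping there could be deliberate. But death and loss to follow-up make observation impossible, whereas this rule gives up observation that could still be made. If stopping is intended, 2.1 and 6.3.1 should say so.

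A second objection is that 8.3 already anticipates censoring, and no section says exited patients are counted as event-free. That is correct: the 9.8%, 9.0% and 7.4% show what one unexcluded handling would do, not what the plan prescribes. Under censoring, that understatement does not arise if exit is unrelated to risk. Exit could be related to risk, but this is not shown. The optional methods change how truncated data are analysed; they do not recover events nobody asked about.

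Third, the effect may be small. This stands. The first two scenarios move the limit by 0.2 and 1.2 percentage points, in a preliminary, unpowered study. The third, with 9 of 30 patients leaving at Month 3, is extreme. If related events cluster soon after the procedures, the loss is smaller than the constant-hazard figures.

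Finally, a site might process the exit as a withdrawal, which would record the reason and allow 30 days of data. That is partial cover and still falls short of 24 months.

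**Conclusion.** The concern holds. Followed exactly, 7.11 truncates planned collection for two of the three primary safety endpoints in any patient who receives non-study SUI treatment before Month 24, and no other section restores it. The post-void residual endpoint is affected only by exits before Month 12.

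The conflict between sections is a matter of text and is firm. That new events would go unsought is a strong inference from how contacts are scheduled. The numerical size is illustrative: it rests on 30 treated patients, assumed exit counts and times, and a constant hazard, and it runs from negligible to material across that range. This should be fixed because it touches the primary objective and is cheap to correct; it does not invalidate the study.

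**What to change.** Reconcile 7.11 with 2.1 and 6.3.1.

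1. In 7.11, keep patients who receive non-study SUI treatment in safety-only follow-up. Record the type and date of that treatment and continue adverse-event collection at the remaining scheduled contacts through the Month 24 call (7.8.7).
2. In 8.3, tabulate related events before and after that date separately. Report the incidence through 24 months in all treated patients and, beside it, the incidence censored at non-study treatment.

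If the sponsor does intend safety follow-up to stop at that point, 2.1 and 6.3.1 should define the horizon as 24 months or non-study SUI treatment, whichever comes first. The number and timing of such exits should then be reported.

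The cost is protocol wording with the usual IRB/REB review and any consent update it requires, two data fields, and contacts that are already scheduled, some of them office visits if the exit is early. The downside is that attribution of later local events may be confounded by the other treatment; the separate tabulation and the censored figure make that visible.
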